6.1.2 Clinical Studies

In the first-in-human study (**Study MB130001**), BMS-986036 was administered by subcutaneous (SC) injection in single and multiple doses for up to 14 days to 72 obese, nondiabetic, healthy adult volunteers.¹⁶ C-terminal intact BMS-986036, the active polypeptide, displayed a half-life of approximately 20 - 24 hours and demonstrated a generally linear PK with 2-fold to 3-fold accumulation following QD dosing. Following single dose administration in the range of 1 mg to 60 mg, the drug was slowly absorbed from the SC injection site (abdomen) into the systemic circulation, with median time to maximum concentration ranging from 24 to 33 hours. Following a single weekly dose of 21 mg, the time to maximum concentration was like that of single doses. BMS-986036 in doses of up to 30 mg QD for up to 14 days was well tolerated and safe; adverse events (AEs) were mild and showed no dose-ordered trends. In the multiple-dosing panels, BMS-986036 increased adiponectin levels in a dose-dependent fashion. Adiponectin increased by 41.7% in the BMS-986036 30 mg QD group; in contrast, it decreased by 28.5% in the placebo group. Adiponectin has been shown to inhibit hepatic stellate cell proliferation and hepatic fibrosis in vitro,¹⁷ and higher levels of adiponectin have been shown to correlate with improvements in fibrosis, as well as steatosis and inflammation.¹⁸ It is therefore likely that an increase in adiponectin in response to BMS-986036 would have beneficial anti-steatotic, anti-inflammatory, and anti-fibrotic effects in NASH patients. BMS-986036 also improved insulin sensitivity, promoted favorable lipid changes (decreased TGs, apolipoprotein B, and LDL cholesterol), and reduced body weight compared to placebo.

BMS-986036 was also studied in two Phase 2 studies. **Study MB130002** was a randomized, double-blind, placebo-controlled, parallel-group, multiple-dose study in obese participants with type 2 diabetes mellitus (T2DM). Over 90% of participants had evidence of underlying

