6.2 Study Rationale

The current study is designed to confirm and extend the results observed in the Phase 1 and 2a studies with BMS-986036. Specifically, this study aims to demonstrate in participants with NASH and compensated cirrhosis, the efficacy of BMS-986036 using histological and noninvasive endpoints, and the safety of BMS-986036 as assessed by AEs, lab results and bone mineral density (BMD) monitoring.

The protocol was planned to randomize approximately 100 participants to 1 of 4 treatment groups (approximately 25 participants per group). This protocol amendment (Version 4.0) reflects that upon close of enrollment, approximately 155 participants were randomized to treatment (approximately 38 participants per group). The increased number of randomized participants occurred following: 1) unexpectedly high enrollment rate in the final month of the enrollment period; 2) several participants who had initially been enrolled into FALCON 1 (MB130-068) were determined (based on central pathology biopsy results) to qualify for FALCON 2 (MB130-069) during the period between the closure of enrollment and completion of randomization; and 3) an unexpected decrease in the actual screen failure rate for subjects entered in the final month of enrollment.

Based on the unmet medical need for patients, the benefit/risk assessment discussed in Section 6.3, and the strict safety monitoring of all participants, the potential clinical benefit outweighs the risks for those who have chosen to participate in this study. No additional revisions are required in Section 9 due to the increased number of randomized participants.

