### **6.3.1 Serum Concentrations**

Serum concentrations of BMS-986036 will be derived from trough (predose) blood samples collected from each participant before the administration of BMS-986036 dosing at each visit. Trough BMS-986036 serum concentrations (in all participants at all visits) [REDACTED]

[REDACTED] will be summarized by treatment and visit for both C-terminal intact and Total BMS-986036.

Sponsor: Bristol-Myers Squibb

Protocol No.: MB130-069

Serum concentrations below LLOQ will be set to missing in the computation of mean concentration values. Descriptive statistics (n, mean, standard deviation (SD), geometric mean, % coefficient variation (CV), median, min, and max) will be used to summarize the serum concentrations at each scheduled time point.

Linear and semi-logarithmic plots of the geometric mean serum concentrations + SD versus scheduled sampling times, overlaid by treatment will be provided for trough concentrations. [REDACTED]

[figure not shown]
[REDACTED] These plots will show study visit and will include a reference line for LLOQ on all plots with just one analyte. The plots will match the summary table results with the exception for time points with no values >LLOQ. For plotting presentation purposes, for time points with no values >LLOQ a value of one-half LLOQ will be used to plot that time point and a corresponding footnote will be added to indicate which time points were affected. All individual subject serum concentration data will be listed.

In addition, individual participant plots of trough concentrations will be presented for all participants and all scheduled time points among the PK population, with C-terminal Intact and total BMS-986036 concentrations on the same plot.

[REDACTED]

Sponsor: Bristol-Myers Squibb

Protocol No.: MB130-069

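### The trough plots in SAP 6.3.1 add an arithmetic SD to a geometric mean, so the error bars have no standard meaning

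*SAP*

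**What the plan says.** SAP 6.3.1 (Serum Concentrations) makes four statements that bear on this point.

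- **Figure:** "Linear and semi-logarithmic plots of the geometric mean serum concentrations + SD versus scheduled sampling times", overlaid by treatment. The same centre and bar serve both axis types.
- **Table:** "Descriptive statistics (n, mean, standard deviation (SD), geometric mean, % coefficient variation (CV), median, min, and max) will be used" at each scheduled time point. The list names no geometric SD and no geometric CV.
- **Link between them:** "The plots will match the summary table results with the exception for time points with no values >LLOQ".
- **Values below LLOQ:** "Serum concentrations below LLOQ will be set to missing in the computation of mean concentration values".

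The section covers both C-terminal intact and Total BMS-986036. Nothing in the visible text of the SAP or protocol defines the SD as geometric or gives a CV for trough concentrations.

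**The concern.** An arithmetic SD measures additive spread around the arithmetic mean. Spread around a geometric mean is multiplicative and is described by the geometric SD, the exponential of the SD of log concentration. Adding one to the other gives a bar end with no standard reading. This holds at any level of variability and needs no assumption about the data.

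Trough concentration is the only PK objective and endpoint in the visible text (Protocol 7.4 and 9.4.3; SAP 3.4 and 4.4), and these figures overlay the dose arms. A reader would take the bar as the spread around the plotted point, and it is not that. What is at stake is the interpretability of a descriptive figure. No test, endpoint, error rate or sample size depends on it.

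**Working it through.** The documents state no trough mean, SD, CV or bar length, so there is no planned figure to reproduce. The check compares the bar as written with a consistent one.

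**Inputs**
- Centre and bar: geometric mean (GM) + SD, with SD as listed in the table (SAP 6.3.1).
- Arm size: about 38 (Protocol 6.2: "approximately 155 participants were randomized to treatment (approximately 38 participants per group").
- Trough CV: not given. Assumed range 30% to 300%, log-normal.
- Half-life, used only to judge which CVs are plausible: C-terminal intact drug "displayed a half-life of approximately 20 - 24 hours" (Protocol 6.1.2), with weekly dosing (168 h).

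**Population bar, GM set to 1**
- SD of log concentration: s = √ln(1 + CV²)
- Arithmetic SD = exp(s²/2) × CV
- Planned bar end = 1 + SD
- Consistent bar end = exp(s), that is, GM × geometric SD

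Example at CV 100%: s = √ln 2 = 0.833, so SD = 1.414 × 1 = 1.414. The planned end is 2.41 and the consistent end is exp(0.833) = 2.30. The end ratio is 2.41/2.30 = 1.05. The length ratio is 1.414/1.299 = 1.09.

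| CV | Planned end | Consistent end | End ratio | Length ratio |
|---|---|---|---|---|
| 30% | 1.31 | 1.34 | 0.98 | 0.92 |
| 50% | 1.56 | 1.60 | 0.97 | 0.93 |
| 79% | 2.01 | 2.01 | 1.00 | 1.00 |
| 100% | 2.41 | 2.30 | 1.05 | 1.09 |
| 150% | 3.70 | 2.96 | 1.25 | 1.38 |
| 200% | 5.47 | 3.56 | 1.54 | 1.75 |
| 300% | 10.49 | 4.56 | 2.30 | 2.66 |

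The two bars agree at a CV of about 79%. Below that the planned bar is short by at most about 8% of its length; above it the bar is too long.

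**What 38 per arm would show.** The sample SD of skewed data is usually below its population value, so simulated log-normal samples of 38 give smaller ratios. With no values below LLOQ, the median end ratio is 0.97 at CV 100%, 1.04 at 150%, 1.12 at 200% and 1.29 at 300%. At CV 100% the bar is too long in only about 40% of samples. In bar length, the medians are 0.90 at CV 50%, 0.95 at 100%, 1.05 at 150% and 1.17 at 200%. If 20% of values are dropped as below LLOQ, the last three become 1.05, 1.14 and 1.23.

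**Which CV applies?** A half-life of 20 rather than 24 h changes a 168-h concentration by a factor of 2^(168/20 − 168/24) = 2^1.4 = 2.64, a log difference of 0.970. The CV this implies depends on what the 20–24 h range represents:
- ±2 SD: s = 0.243, CV about 25%
- ±1 SD: s = 0.485, CV about 52%
- one SD in total: s = 0.970, CV about 125%

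Alternatively, 168 h is 4.85 to 5.82 elimination time constants (168 × ln 2 / half-life). An assumed between-participant CV in elimination rate of 10% then gives a trough CV of 52% to 64%, and one of 15% to 25% gives 84% to 271%. These ranges fall on both sides of 79%.

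**The case against.** **The SD may be geometric.** The SAP never calls its SD arithmetic, some nearby text is redacted, and SAP Appendix 2 sends figure layouts to a separate shell document. In the list, % CV comes straight after the geometric mean, so it may be a geometric CV, from which a geometric SD could be recovered. The point about % CV stands: its type is ambiguous, and it cannot be assumed to be arithmetic. For the SD, the arithmetic reading remains much the more natural. It is the only SD listed, it follows the arithmetic mean, the plot uses a plus sign, and the plots must match the table. If a geometric SD was meant, the SAP still has to say so.

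**The bars are too long.** A reader might infer this, because the sample is taken about 7 to 8.4 half-lives after the dose, where small differences in elimination are magnified. The documents do not support it. They give no trough CV, and do not say that the quoted half-life range is between-participant spread. They give no half-life for Total drug. Protocol 6.1.2 also reports a median time to maximum of 24 to 33 h, so not all of the 168 h is elimination.

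**The plots are the main PK display and will blur dose separation.** A reader might infer this too, but it does not follow. The table, individual participant plots and listings also serve the trough objective, and exposure-response work uses modelled exposures under a separate plan (Protocol 9.5.4). The geometric means are unaffected by the choice of bar. Doses rise in two-fold steps, with exposure reported as generally proportional between 20 and 40 mg (Protocol 6.2.2). At a CV of 79% a correct geometric SD is already about 2, so a correct bar would also reach the next dose's geometric mean if proportionality holds.

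**Conclusion.** Wrong as written, and minor. Adding the listed SD to a geometric mean gives an error bar with no standard interpretation, and no visible text corrects it.

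The numerical effect is modest for an arm of about 38: a typical bar-end error of roughly −3% at CV 100%, +4% at 150%, +12% at 200% and +29% at 300%. These figures assume log-normal troughs and no values below LLOQ. The population ratios of 1.25 to 2.30 at CV 150% to 300% overstate what a sample of this size would typically show. Since the trough CV is unknown, the direction of the error in this trial is unknown as well.

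The conclusion that the bars are mismatched rests on reading the listed SD as arithmetic, a strong inference but not an explicit statement. The effect is confined to descriptive PK figures; the primary analysis, alpha and power are untouched.

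**What to change.** In SAP 6.3.1:

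1. Plot the geometric mean with limits at geometric mean × geometric SD and geometric mean ÷ geometric SD, on both the linear and the semi-logarithmic plots.
2. Add to the summary table the geometric SD, or the geometric CV% = 100 × √(exp(s²) − 1), where s is the SD of log concentration. The figure and table then still agree.
3. Label the existing SD and % CV as arithmetic or geometric.

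Plotting the arithmetic mean with the arithmetic SD would also be internally consistent, if the sponsor prefers that.

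The cost is a wording change in the SAP, a matching edit to the table and figure shells, and minor programming. No new data are needed.

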## 6.4 Exploratory Analyses

Analyses for exploratory endpoints (including biomarkers) will be performed using the mITT or safety populations. Categorical and continuous data will be summarized descriptively as presented in SAP [Section 6.5](#).

Exploratory dichotomous response variables will be summarized in a manner similar to that used for the primary and secondary efficacy analyses:

- Assessment of NASH CRN Fibrosis Score at Week 48
  - Proportion of participants with  $\geq 1$  stage improvement
  - Proportion of participants with  $\geq 2$  stage improvement
  - Proportion of participants with  $\geq 2$  stage improvement without worsening of NASH
  - Proportion of participants with NASH resolution
  - Proportion of participants with NASH improvement
- Assessment of Ishak Fibrosis Score at Week 48
  - Proportion of participants with  $\geq 1$  stage improvement
  - Proportion of participants with  $\geq 2$  stage improvement
- Assessment of CPA at Week 48
  - Proportion of participants with any improvement
- Hepatic fat fraction as measured using MRI-PDFF at Week 24 and Week 48
  - Proportion of subjects with  $\geq 30\%$  relative reduction,  $\geq 20\%$  relative reduction,  $\geq 10\%$  relative reduction, and  $\geq 5\%$  absolute reduction
- Liver stiffness as determined by MRE at Week 24 and Week 48
  - Proportion of subjects with  $\geq 19\%$  reduction
  - Proportion of subjects with  $\geq 15\%$  reduction
- Fibroscan elastography results at Week 48
  - Proportion of subjects with any improvement

In addition, summaries of  $\geq 1$  stage improvement, no change, and worsening will be tabulated and graphically presented for NASH CRN Fibrosis Score, Ishak Fibrosis Score, and NAS Total at Week 48. Participants without a Week 48 (or ET result) will be classified into the "Worse" category for these exploratory summaries.

Similarly to the primary and secondary efficacy endpoints, for exploratory endpoints based off the liver biopsy, the Week 48 result or ET biopsy will be used for Week 48 derivations. Participants without a Week 48 or ET biopsy will be classified as non-responders for liver biopsy endpoints at Week 48. Early termination visits for non-biopsy endpoints such as imaging and biomarkers may occur at other time points and will not

Sponsor: Bristol-Myers Squibb

Protocol No.: MB130-069

be summarized together with Week 48. For non-biopsy endpoints, ET will be summarized separately in the summary tables.

For continuous endpoints the analysis of covariance (ANCOVA) models will be used to explore changes from baseline that include fixed factors for the treatment group and the corresponding covariate for baseline value for the following:

- Quantitative measurements of fibrosis and fat on biopsy
  - Assessment of qFibrosis using digital pathology
  - Assessment of CPA
  - Assessment of fat and alpha-SMA by morphometry
- Hepatic fat fraction as measured using MRI-PDFF
- Noninvasive measures of fibrosis and/or cirrhosis
  - Liver stiffness as determined by MRE
  - Fibroscan elastography results
  - APRI, FIB-4, and NAFLD scores
- Exploratory biomarkers
  - Transaminases ALT and AST
  - PRO-C3

A repeated measures analysis will model changes from baseline for each of the exploratory endpoints separately for data collected at planned visits using restricted maximum likelihood estimations. The model will include treatment group, visit, baseline value, treatment \* visit and baseline stratification factors as fixed effects. An unstructured covariance matrix will be used to represent the correlation of the repeated measures within each subject. This model will be used to provide point estimates for the treatment differences, standard errors for the differences, and corresponding 2-sided 95% confidence intervals for mean change from baseline at each time point. Statistical inferences for comparing treatment groups will utilize Kenward-Rodgers Degrees of Freedom.

Other biomarkers will be descriptively summarized by time point and will include percent change from baseline in addition to change from baseline.

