8.3.1 Inclusion Criteria

1. Signed written informed consent
 - a) Participants must be willing to participate in the study and sign the informed consent form(s) (ICF[s])
 - b) Participants (and caregivers as applicable) must be willing and able to complete all study-specific procedures and visits
2. Liver biopsy performed within 6 months (26 weeks) prior to the Screening Period. Biopsy performed prior to ICF must be available to the central reader prior to randomization. If historical biopsy is not available, a liver biopsy will be performed during the Screening Period (see Section [8.5.1.1](#)). Biopsy must be consistent with NASH and cirrhosis according to the NASH CRN classification, as assessed by the central reader.
3. Participants taking anti-diabetic, anti-obesity, or anti-dyslipidemic medications must have been on stable regimens for at least 3 months (12 weeks) (6 weeks for statins) prior to and during the Screening Period. The investigator may contact the medical monitor regarding the stability of a participant's regimen when determining eligibility for study participation. Participants taking vitamin E at doses ≥ 800 IU/day must have been on stable doses for at least 6 months (26 weeks) prior to and during the Screening Period. Vitamin E treatment (≥ 800 IU/day) must not have been initiated after the qualifying liver biopsy was performed.
4. Age and reproductive status
 - a) Men or women 18 to 75 (inclusive) years of age
 - b) Women of childbearing potential (WOCBP) must have a negative pregnancy test (minimum sensitivity 25 IU/L or equivalent units of human chorionic gonadotropin) within 24 hours prior to the start of study medication
 - c) Women must not be breastfeeding at any time during the study

- d) WOCBPs must agree to follow instructions for method(s) of contraception for the duration of treatment (BMS-986036 or placebo) plus 5 half-lives of study medication (5 days) plus 30 days (duration of ovulatory cycle) for a total of 35 days after the end of the Double-Blind Treatment Period
- e) WOCBPs who are continuously not heterosexually active are exempt from contraceptive requirements but must undergo pregnancy testing as described in the Schedule of Activities in Section 1

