8.3.8.2 Rescreening

This study will permit the rescreening of a participant who has discontinued the study as a pre-treatment failure (i.e., the participant has not been randomized/has not been treated). Consultation with the medical monitor may be needed to identify whether rescreening is clinically relevant. If rescreened, the participant must sign a new ICF.

In the event that histologic evaluation of the biopsy of an otherwise qualified participant results in a diagnosis of NASH with stage 3 fibrosis, that individual is not eligible for the present study (MB130-069) but may be considered for enrollment under protocol MB130-068 (A Phase 2b Randomized, Double-Blind, Placebo-Controlled Study Evaluating

the Safety and Efficacy of BMS-986036 (PEG-FGF21) in Adults with Nonalcoholic Steatohepatitis [NASH] and Stage 3 Liver Fibrosis). Laboratory parameters and/or assessments that were collected as Screening procedures for this study (MB130-069; [Table 1](#) in Section 1) may be utilized for the same purpose for MB130-068.

Conversely, in the event that histologic evaluation of the biopsy of an otherwise qualified participant for MB130-068 results in a diagnosis of NASH with cirrhosis, that individual is not eligible for the MB130-068 study but can be considered for enrollment under the present study (MB130-069). Laboratory parameters and/or assessments that were collected as Screening procedures for MB130-068 may be utilized for the same purpose (Table 1 in Section 1) in this study (MB130-069).

For participants who are rescreened, consult with the medical monitor to confirm which parameters and/or assessments that were collected as part of the original Screening Period procedures may be utilized.

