#### 4.5 Exploratory Endpoints

Exploratory endpoints include the following:

- Quantitative measurements of fibrosis and fat on biopsy
  - Assessment of NASH CRN Fibrosis Score at Week 48
    - Proportion of participants with  $\geq 1$  stage improvement
    - Proportion of participants with  $\geq 2$  stage improvement
    - Proportion of participants with  $\geq 2$  stage improvement without worsening of NASH
    - Changes in Fibrosis (as expressed by Shift from baseline)
    - Proportion of participants with  $\geq 1$  stage improvement, no change, or worsening
  - Assessment of Ishak Fibrosis Score at Week 48
    - Proportion of participants with  $\geq 2$  stage improvement
    - Changes in Fibrosis (as expressed by Shift from baseline)
    - Proportion of participants with  $\geq 1$  stage improvement, no change, or worsening
  - Assessment of qFibrosis using digital pathology at Week 48
    - Absolute, percent change, and change from baseline
  - Assessment of CPA at Week 48
    - Proportion of participants with any improvement
    - Absolute, percent change, and change from baseline
  - Assessment of fat and alpha-SMA in stained tissue by morphometry at Week 48
    - Absolute, percent change, and change from baseline
- Assessment of NAS score at Week 48
  - Changes in NAS (as expressed by shift from baseline, for each individual NAS components (Steatosis, inflammation, Ballooning) as well as Total score)
  - Proportion of participants with improvement, no change, or worsening in NAS Total
- Hepatic fat fraction as measured using MRI-PDFF at Week 24 and Week 48
  - Absolute, percent change, and change from baseline
  - Proportion of subjects in each treatment group with  $\geq 30\%$  relative reduction,  $\geq 20\%$  relative reduction,  $\geq 10\%$  relative reduction, and  $\geq 5\%$  absolute reduction
- Noninvasive measures of fibrosis and/or cirrhosis
  - Liver stiffness as determined by Magnetic Resonance Elastography (MRE) at Week 24 and Week 48
    - Absolute, percent change, and change from baseline
    - Proportion of subjects in each treatment group with  $\geq 19\%$  or  $\geq 15\%$  reduction
  - Fibroscan elastography results at Week 48
    - Absolute, percent change, and change from baseline
    - Proportion of subjects in each treatment group with any decrease by time point

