## 5.0 Analysis Populations

- Enrolled Population: All participants who sign informed consent.
- Randomized Population: All participants who are randomized, analyzed as per randomized treatment.
- Modified intent-to-treat (mITT) Population: All participants who are randomized and receive at least 1 dose of study medication, analyzed according to randomized treatment. All primary efficacy analyses will be conducted using this population.
- As Treated (Safety) Population: All participants who are randomized and receive at least 1 dose of study medication, analyzed according to treatment actually received. This population will be essentially the same as the mITT unless a participant received an incorrect treatment, i.e., a treatment different from what he/she was randomized to. All safety analyses will be conducted using this population.
- Pharmacokinetic (PK) Populations: All randomized participants who receive at least 1 dose of BMS-986036 and have any available concentration-time data. Available concentration-time data includes results that may be less than the lower limit of quantification (LLOQ). [REDACTED]

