#### Fibrosis

#### NASH CRN Fibrosis

Fibrosis is staged separately from NAS on a 0-4 scale: 0 (none); 1 (perisinusoidal or periportal fibrosis); 2 (perisinusoidal and portal/periportal fibrosis); 3 (bridging fibrosis); 4 (cirrhosis).

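### Missing biopsies are counted as Worse in the exploratory fibrosis summaries, although eligible participants enter at the top NASH CRN stage and cannot be observed to worsen

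*SAP*

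**What the plan says.** SAP 4.5 lists three-way exploratory endpoints. For NASH CRN and Ishak fibrosis the categories are at least one "stage improvement, no change, or worsening". For the activity score the endpoint is "Proportion of participants with improvement, no change, or worsening in NAS Total".

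SAP 6.4 turns these into displays, with improvement, "no change, and worsening will be tabulated and graphically presented for NASH CRN Fibrosis Score, Ishak Fibrosis Score, and NAS Total at Week 48". The rule for a missing biopsy follows: "Participants without a Week 48 (or ET result) will be classified into the 'Worse' category for these exploratory summaries".

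Three other places fix where participants start on the NASH CRN fibrosis scale:

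- Protocol 8.3.1, inclusion criterion 2: "Biopsy must be consistent with NASH and cirrhosis according to the NASH CRN classification, as assessed by the central reader".
- Protocol 8.3.8.2, on a screening biopsy that shows a "diagnosis of NASH with stage 3 fibrosis, that individual is not eligible for the present study (MB130-069").
- SAP 8.6, which stages fibrosis from 0 to 4 and ends the scale with "3 (bridging fibrosis); 4 (cirrhosis").

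The mITT population in SAP 5.0 is "All participants who are randomized and receive at least 1 dose of study medication, analyzed according to randomized treatment". It has no condition on the baseline stage.

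**The concern.** A row or bar labelled as worsening will be read as fibrosis that progressed on biopsy. On NASH CRN fibrosis no eligible participant can progress, because all of them start at the highest stage. The bar would measure missing biopsies, and a difference between arms in its height would be a difference in missingness, not in disease course.

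The rule is also not a worst-case value in the usual sense. From stage 4 the worst outcome that can be observed is no change, so the rule puts missing participants in a category that their biopsied counterparts cannot reach.

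Missing results are foreseeable. Protocol 8.5.1.1 asks a participant who leaves the study before Week 20 only to consider an early-termination biopsy, and the SAP itself plans summaries of visits missed because of COVID-19 (2.5 and 6.5.7).

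**Working it through.** The plan states no missing-biopsy rate and no expected share worsening, so there is no figure of its own to reproduce here. The check has two parts.

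**1. Can an observed biopsy fall in the worsening category?** For each scale, count the post-baseline scores that are higher than the baseline score.

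| Scale (SAP 8.6) | Baseline | Higher scores available | Content of the Worse category |
|---|---|---|---|
| NASH CRN fibrosis, 0-4 | 4 (entry requirement) | none (4 - 4 = 0 stages) | missing results only |
| Modified Ishak, 0-6 | 5 | stage 6 | observed worsening and missing results |
| Modified Ishak, 0-6 | 6 | none | missing results only |
| NAS Total, 0-8 | 0 to 7 | at least one | observed worsening and missing results |
| NAS Total, 0-8 | 8 | none | missing results only |

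The NASH CRN result holds for every eligible participant. The exception is a participant randomized in error below stage 4. That person stays in mITT once dosed and could be observed to worsen.

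**2. How large could the effect be?** Inputs: about 155 randomized and about 38 per arm (Protocol 6.2; SAP 2.1). The missing rates are assumptions.

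- Participants labelled as worse without a biopsy = number randomized x missing rate.
- Height of the NASH CRN bar = missing participants in the arm / 38.

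| Assumed missing | Of 155 | Of 38 | Whole participants per arm | NASH CRN Worse bar under the rule | Observable from eligible participants |
|---|---|---|---|---|---|
| 5% | 7.8 | 1.9 | 2 | 2/38 = 5.3% | 0% |
| 10% | 15.5 | 3.8 | 4 | 4/38 = 10.5% | 0% |
| 15% | 23.3 | 5.7 | 6 | 6/38 = 15.8% | 0% |
| 20% | 31.0 | 7.6 | 8 | 8/38 = 21.1% | 0% |

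One missing biopsy moves its arm's bar by 1/38 = 2.6 percentage points.

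**What does not move.** SAP 6.1.1 and 6.4 already count a missing biopsy as non-response for the dichotomous biopsy endpoints. Moving such participants from Worse to Missing leaves the improvement count and its mITT denominator as they are, so no responder proportion or test changes.

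**The case against.** The strongest reply is that this is an openly stated convention, in line with the non-responder rule beside it, in a descriptive summary on which no test or decision rests. Observed change is reported elsewhere: SAP 4.5 plans shift summaries for all three scores, and SAP 6.1.1 plans shift tables for NAS and NASH CRN fibrosis and a listing of all biopsy results. SAP Appendix 2 leaves the displays to a separate shell document, where a label or footnote might already say that missing results are included. All of this stands, and it is why the point is minor. It does not correct the rule, which directs missing results into a category that means something else.

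Four narrower objections:

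- *Baseline re-read.* If baseline slides were read again alongside the Week 48 slides, the analysed baseline of an eligible participant could be below 4. Neither document states a re-read, so the ceiling argument assumes that the eligibility read is the analysed baseline.
- *Ishak ceiling.* From Ishak 6 the same ceiling applies. This is correct and adds to the point.
- *Who is summarized.* SAP 7.1 speaks of efficacy data on participants who have completed a biopsy. Read literally, that leaves no missing results to classify. The specific rule in SAP 6.4 would then have no purpose, so 6.4 more likely governs, but the denominator should be stated.
- *Missingness may be low.* Protocol 8.5.1.1 provides for an early-termination biopsy from Week 20 onward and lets a late biopsy be done as close to schedule as possible. SAP 7.1 counts biopsies delayed to between Week 48 and Week 52 as Week 48. These limit missingness but do not remove it.

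**Conclusion.** The concern holds, as a minor point. For eligible participants the NASH CRN fibrosis category for worsening can contain only missing results, and for Ishak and NAS Total it cannot be read as observed worsening. At an assumed 5-20% missing, the NASH CRN bar would stand at about 5-20% where biopsies from eligible participants could give only 0%.

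The conclusion rests on the eligibility read being the analysed baseline and on no participant being randomized in error below stage 4. The size rests on the assumed missing rate. Whether the shells already carry a clarifying note is not known.

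**What to change.** Replace the missing-biopsy sentence in SAP 6.4 with:

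> In these three summaries and graphs, participants without a Week 48 or ET biopsy result will be shown in a separate Missing category, with the mITT population as denominator; a footnote will state that worsening from NASH CRN stage 4 is not possible. The non-responder rule below continues to apply to the dichotomous biopsy endpoints.

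The same footnote could usefully say that Ishak stage 6 is also a ceiling. The denominator is named because SAP 6.4 allows either the mITT or the safety population, SAP 6.5 lets by-visit denominators be adjusted, and SAP 7.1 refers to participants with a completed biopsy.

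The cost is one replaced SAP sentence, recorded in the change log that SAP 1.0 provides for before database lock, and one extra row or bar segment with a footnote in the shells. The three existing categories stay, so SAP 4.5 needs no edit. No new data are needed, and no test or non-responder imputation changes.
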